Appendix A: Schedule of Assessments and Timing of Sample Collection and Procedures for the Treatment Period.....	60
Appendix B: Clinical Laboratory Analytes	64

LIST OF TABLES

Table 1. Schedule of Assessments	60
Table 2. Timing of Sample Collection and Procedures for the Treatment Period.....	63

LIST OF FIGURES

Figure 1. Enrollment Schematic: Parallel Design 25

LIST OF ABBREVIATIONS AND DEFINITION OF TERMS

Abbreviation	Definition
AE	Adverse event
CF	Cystic fibrosis
CFR	Code of Federal Regulations
CRA	Clinical Research Associate
CT	Computerized tomography
CTA	Clinical Trial Authorisation
CTCAE	Common Terminology Criteria for Adverse Events
DSMB	Data Safety Monitoring Board
ECG	Electrocardiogram
eCRF	Electronic case report form
EDC	Electronic data capture
EIU	Exposure In Utero
EOS	End of Study
ET	Early Termination
FDA	Food and Drug Administration
FEF ₂₅₋₇₅	Forced expiratory flow between 25% and 75% of the forced vital capacity
FEV ₁	Forced expiratory volume
FVC	Forced vital capacity
GCP	Good Clinical Practice
GLI	Global Lung Initiative
HR	Heart rate
HRCT	High-resolution computerized tomography
ICF	Informed consent form
ICH	International Council for Harmonisation
IEC	Independent Ethics Committee
IRB	Institutional Review Board
LCQ	Leicester Cough Questionnaire
NCFB	Non-cystic fibrosis bronchiectasis
NIMP	Non-investigational medicinal product
PFU	Plaque-forming units
PRO	Patient-reported outcome
QOL-B	Quality of Life-Bronchiectasis
QTc	Heart rate-corrected QT interval
SAE	Serious adverse event
SAP	Statistical Analysis Plan
SpO ₂	Oxygen saturation
SUSAR	Suspected Unexpected Serious Adverse Reaction
ULN	Upper limit of normal

1 INTRODUCTION AND BACKGROUND INFORMATION

1.1 Introduction

Armata Pharmaceuticals, Inc. (Armata, the Sponsor) is developing a proprietary multi-phage therapeutic candidate (AP-PA02) for the management of non-cystic fibrosis bronchiectasis (NCFB) subjects with chronic respiratory infections associated with *Pseudomonas aeruginosa*.

1.1.1 Non-Cystic Fibrosis Bronchiectasis and Chronic *Pseudomonas aeruginosa* Infection

[figure not shown]
[REDACTED]

[REDACTED]

[figure not shown]
[REDACTED]

1.1.2 Phages as Antimicrobials

[figure not shown]
[figure not shown]
[REDACTED]

1.1.2.1 Mechanisms of Action of Phages

1.2 Rationale

1.3 Risk/Benefit

1.3.1 Study Benefits

1.3.1.1 Known Benefits

The clinical benefit of AP-PA02 remains to be established.

1.3.1.2 Potential Benefits

Subjects participating in this study will receive close medical attention and may have benefit regarding the clinical course of their chronic *P. aeruginosa* infection. Results from the proposed study may be useful in developing a new antimicrobial therapy for *Pseudomonas* infections that can be administered at home without the cost or logistical challenges posed by intravenous therapy or the collateral damage to the gut microbiota with systemic therapy.

1.3.2 Study Risks

1.3.2.1 Known Risks

There is limited human experience with AP-PA02. No adverse drug reactions related to study drug have been identified so far.

1.3.2.2 Potential Risks

All therapies have the potential to cause adverse experiences. The risks associated with blood sampling for safety or pharmacokinetic purposes are limited and the volume of blood needed is well below the acceptable limits for adults. Study intervention will be provided in addition to, not in replacement of, standard of care supportive and symptomatic therapy.

The risks of nebulized phage therapy may include bronchial irritation and/or immune response to phages. As such, subjects will be monitored closely on Day 1 of dosing under clinical supervision with regularly scheduled vital sign, spirometry, and AE assessments. In addition, sentinel dosing, individual subject stopping criteria, and study stopping criteria are included as part of the study conduct.

2 STUDY OBJECTIVE

The primary objective is to evaluate the efficacy, safety, and phage kinetics of multiple inhaled doses of AP-PA02 administered as monotherapy and administered in combination with inhaled antibiotics compared to placebo and inhaled antibiotics alone.

3 STUDY DESCRIPTION

3.1 Summary of Study Design

This is a Phase 2, double-blind, randomized, placebo-controlled study to evaluate the safety, tolerability, and efficacy of AP-PA02 administered by inhalation.

The study will evaluate AP-PA02 administered by inhalation in medically stable NCFB subjects with chronic pulmonary *P. aeruginosa* infection at the time of Screening. A total of 24 eligible subjects who have not received an antipseudomonal inhaled antibiotic for a minimum of 3 months prior to Visit 1 will be randomized to Cohort A to receive either AP-PA02 or placebo (2:1 ratio) administered via inhalation. A total of 24 eligible subjects who have received an antipseudomonal inhaled antibiotic for a minimum of 3 months prior to Visit 1 will be randomized to Cohort B to receive either AP-PA02 plus their current antipseudomonal inhaled antibiotic or placebo plus their current antipseudomonal inhaled antibiotic (2:1 ratio) administered via inhalation. Cohort A and Cohort B will be run in parallel. Up to an additional 2 optional cohorts (up to 30 subjects in each cohort) may be included to evaluate different doses and durations of treatment after Data Safety Monitoring Board (DSMB) review. Prior to DSMB review, the maximum study treatment duration will be 10 days for Cohorts A and B and up to 28 days for the optional cohorts.

For Cohort A, eligible subjects will be randomized at the Baseline Visit to receive 1 fractionated dose of AP-PA02 or placebo (1 dose distributed over 2 administrations given 6 hours apart on the same day on Day 1 and 10-12 hours apart each day on the remaining days) for 10 days (Study Days 1 through 10). Subjects will return to the clinic on Days 1, 5, and 10 (Visit 1/Day 1, Visit 2/Day 5, and Visit 3/Day 10) of study drug dosing and approximately 24 hours post last AP-PA02 or placebo dose for safety evaluations and phage recovery sampling, and again 7, 14, and 28 days after the last dose of AP-PA02 or placebo (Visit 4/Day 11, Visit 5/Day 17, Visit 6/Day 24, and Visit 7/Day 38). Subjects will be followed for safety for 4 weeks after the last dose of study drug.

For Cohort B, eligible subjects will be randomized at the Baseline Visit to receive 1 fractionated dose of AP-PA02 or placebo (1 dose distributed over 2 administrations given 6 hours apart on the same day on Day 1 and 10-12 hours apart each day on the remaining days) for 10 days (Study Days 1 through 10) with their current inhaled antipseudomonal antibiotic administered for 28 days (10 days of study drug treatment plus an additional 18 days). Subjects will return to the clinic on Days 1, 5, and 10 (Visit 1/Day 1, Visit 2/Day 5, and Visit 3/Day 10) of study drug dosing and approximately 24 hours post last AP-PA02 or placebo dose for safety evaluations and phage recovery sampling, and again 7, 14, and 28 days after the last dose of AP-PA02 or placebo (Visit 4/Day 11, Visit 5/Day 17, Visit 6/Day 24, and Visit 7/Day 38). Subjects will be followed for safety for 4 weeks after the last dose of study drug.

[figure not shown]
The first 2 subjects in Cohorts A and B will consist of 1 active and 1 placebo subject. Both subjects will be observed for at least 2 days after dosing, and if there are no Grade 2 or greater AEs assessed as treatment-related, dosing for the remaining subjects will proceed.

Safety evaluations after the first dose for each cohort will include vital signs (blood pressure, heart rate [HR], respiratory rate, and body temperature), oxygen saturation (SpO₂), 12-lead electrocardiogram (ECG), and spirometry. The schedule of subsequent assessments during and after treatment is detailed in the Schedule of Assessments ([Appendix A](#)).

Visit 7/Day 38 will be the End of Study (EOS) Visit. Safety and an anti-phage antibody titer will be performed at the EOS Visit.

Figure 1 displays the enrollment schematic.

Figure 1. Enrollment Schematic: Parallel Design

abx = antibiotic; BID = twice daily; EOS = End of Study; N = number of subjects; NCFB = non-cystic fibrosis bronchiectasis; *P. aeruginosa* = *Pseudomonas aeruginosa*.

3.1.1 Safety Monitoring

If subjects experience any acute AEs post-dose administration (regardless of causal relationship to study drug), the Investigator will determine if they may be observed in the clinic and discharged that day or, in consultation with the Medical Monitor, if they need to be admitted to the hospital for additional observation and/or treatment.

All subjects will be followed for 28 days after the last dose of AP-PA02 or placebo for safety and phage recovery profile, or until resolution or stabilization of AEs or study-related AEs.

AEs Grade 3 or higher assessed by the Investigator as related to study treatment will be reported to the Medical Monitor within 24 hours of awareness. The DSMB will constitute 3 independent physicians with experience in clinical studies and in the management of subjects with chronic pulmonary disease complicated by chronic infections. All DSMB procedures will be documented in a DSMB Charter which will be approved by all members and the Sponsor. The DSMB will conduct unblinded scheduled reviews of all available data after approximately 10% and/or after approximately 50% enrollment. They will also conduct ad hoc reviews as needed. Following each review, they will make recommendations regarding the conduct of the study, including, but not limited to, continuing as planned, modifying procedures, pausing enrollment and/or treatment pending additional information, and discontinuing the study. The planned dose levels and dosing duration after DSMB review may be modified and/or additional cohorts may be added based on

emerging information from the current study as well as other ongoing studies. The highest total daily dose will not exceed 4×10^{12} PFU and dosing duration will not exceed 28 days.

3.2 Study Indication

The indication for this study is management of NCFB subjects with chronic respiratory infections associated with *P. aeruginosa*.

4 SELECTION AND WITHDRAWAL OF SUBJECTS

4.1 Inclusion Criteria

Subjects who meet all of the following criteria will be considered eligible for enrollment in the study:

1. Are able and willing to comply with the Protocol and provide signed informed consent prior to any study-specific procedures;
2. Are male or female ≥ 18 years old;
3. Have a body mass index of $\geq 16.5 \text{ kg/m}^2$;
4. Have findings consistent with bronchiectasis per computerized tomography (CT) (or high-resolution CT [HRCT]);

Note: A CT or HRCT that demonstrates the above criterion is required during Screening or the Screening Period unless such an examination has been performed within the last 5 years and meets the above criterion.

5. Have microbiological evidence of pulmonary *P. aeruginosa* infection from a sputum sample within the last 24 months. Sputum cultures may be repeated on up to 3 occasions during the Screening Period to document *P. aeruginosa* presence if the initial sputum culture is negative;
6. Are willing and able to provide an induced sputum sample at Screening or during the Screening Period and at designated time points during the study and are willing and able to provide a spontaneously expectorated or induced sputum at all other time points;
7. Have $\geq 10^4$ colony-forming units of *P. aeruginosa* per gram of induced sputum obtained at Screening or during the Screening Period. Up to 3 specimens may be collected to meet this criterion;
8. Have forced expiratory volume (FEV₁) $\geq 35\%$ of predicted normal for age, gender, race, and height (using Global Lung Function Initiative standards) at Screening (regardless of the timing of the most recent prior administration of short-acting bronchodilator) or during the Screening Period;
9. Have, at the Baseline Visit, stable lung function, as determined by the Investigator, provided that the FEV₁ at the Baseline Visit has not decreased by more than 10% compared to the FEV₁ measured at Screening or during the Screening Period;
10. Have no acute infection or exacerbation of primary disease, as determined by the Investigator, prior to randomization and first dose of study drug;
11. Are able to reproducibly perform spirometry per American Thoracic Society/European Respiratory Society Standards;
12. Have past experience administering inhaled antibiotics and/or feel comfortable administering inhaled antibiotics and/or have a caregiver that is comfortable administering inhaled antibiotics to the subject;
13. For Cohort A, have not received chronic inhaled antipseudomonal antibiotic regimen for at least 3 months prior to Visit 1. For Cohort B, have received chronic inhaled antipseudomonal antibiotic regimen for at least 3 months prior to Visit 1;

14. Are able to comply with study visits and study procedures as judged by the Investigator;
15. Have a negative serum pregnancy test at Screening and a negative urine pregnancy test at the Baseline Visit, with results known prior to randomization and first dose of study drug, if a woman of childbearing potential (as defined in [Section 5.6.4](#));
16. Must agree to use a highly effective method of birth control (defined as those, alone or in combination, that result in a low failure rate [ie, less than 1% per year]) from Screening through 60 days following the last dose of study drug if female or female partner of male subjects, of childbearing potential; and
17. Must agree to use barrier contraception (ie, condoms) from Day 1 through 60 days following the last dose of study drug if male. Male subjects must refrain from donating sperm throughout the study and until 60 days after the last dose of study drug.

4.2 Exclusion Criteria

Subjects who meet any of the following criteria will not be eligible for enrollment in the study:

1. Have previously received 1 or more doses of AP-PA02 in any context, including, but not limited to, prior participation in study AP-PA02-101, prior enrollment in this study, or emergency use (with or without prior authorization);
2. Have a history of lung transplantation;
3. Have a history of primary or acquired immunodeficiency syndromes, including, but not limited to, hypogammaglobulinemia and common variable immunodeficiency;
4. Have a history of cystic fibrosis;
5. Have a history of α 1-antitrypsin deficiency;
6. Have a history of pulmonary malignancy (primary or metastatic) or any other malignancy requiring treatment (including, but not limited to, chemotherapy, radiation therapy, or immunotherapy) within 1 year prior to Screening or anticipated during the study period (Exceptions: Basal cell carcinoma of the skin and carcinoma in situ of the cervix surgically excised and assessed as definitely removed);
7. Have, at Screening or during the Screening Period, either of the following findings:
 - A personal history or subject-reported family history of prolonged QT syndrome; or
 - Severe cardiovascular disease such as severe uncontrolled hypertension, unstable ischemic heart disease or cardiac arrhythmia and any other cardiac conditions that would confound the evaluation of safety in the opinion of the Investigator.
8. Have a history of hemoptysis meeting either of the following criteria:
 - Within the 6 months prior to Screening, was hospitalized for management or evaluation of hemoptysis; or
 - Within the 3 months prior to Screening, had hemoptysis totaling greater than 30 mL in a single day.
9. Have, within the 3 months prior to Screening, used supplemental oxygen during the day while at rest;

10. Have, within the 3 months prior to Screening, lost more than 10% of their body weight;
11. Have, within the 2 months prior to Screening, participated in any clinical study involving an investigational drug, an investigational device, or any systemic antibiotic;
Note: For systemic drugs or antibiotics with a half-life >12 days, the exclusion period is 5 half-lives.
12. Have, within the 30 days prior to Screening, received any intravenous, intramuscular, or oral antipseudomonal antibiotic (Exception: Chronic oral macrolide treatment with a stable dose is permitted);
Note: Inhaled antibiotic use for chronic suppression of *P. aeruginosa* is acceptable for subjects enrolling in Cohort B.
13. Have, within 30 days prior to Screening, had changes in either the treatment regimen or initiation of treatment with any of the following medications: oral macrolides (eg, azithromycin, erythromycin, or clarithromycin), hypertonic saline, mucolytics, bronchodilator medications, or oral corticosteroids;
14. Have, within the 30 days prior to Screening, received a course of any systemic antibiotics (by any route) for a new active infection at any site, unless assessed as fully resolved and not clinically significant by the Investigator with concurrence of the Medical Monitor;
15. Are, at Screening or during the Screening Period, receiving treatment for active pulmonary infection due to any of the following pathogens: nontuberculous mycobacteria, *Staphylococcus aureus*, *Burkholderia cepacia* complex, *Aspergillus* species, or endemic mycoses;
16. Are receiving treatment for allergic bronchopulmonary aspergillosis;
17. Have, within 30 days prior to Screening, received either a systemic corticosteroid at a dose equivalent to >20 mg/day of prednisone (including every other day dosing of >40 mg equivalent) or any immunosuppressive medication or biologic for the treatment of inflammatory or autoimmune disease;
18. Have history of AIDS (human immunodeficiency virus positive with AIDS-defining condition and/or CD4 count <200 cells/mm³, and/or unstable detectable viral load) or chronic severe liver disease due to hepatitis B virus (HBV) or C virus (HCV) with liver biopsy or radiologic evidence of cirrhosis. If neither of these options are feasible to confirm disease status, ribonucleic acid testing should be performed by the Investigator at Screening;
19. Are, at Screening or during the Screening Period, breastfeeding or planning to become pregnant or breastfeed within the next 2 months;
20. Have, at Screening or during the Screening Period or at the Baseline Visit prior to randomization and first dose of study drug, vital signs considered to be clinically significant by the Investigator, endangering the safe participation of the subject in the study;
21. Have, at Screening or during the Screening Period, abnormal laboratory results. Subjects with values outside of the normal range may be permitted if the value is not clinically significant in the opinion of the Investigator with concurrence from the study Medical Monitor and/or Sponsor designee.

Note: Abnormal laboratory results may be repeated once and only once at the discretion of the Investigator.

22. Have, in the opinion of the Investigator, any acute or chronic medical, psychiatric, or behavioral condition or laboratory abnormality such that any of the following apply: the subject is considered not medically stable or in any other way not suitable for the study; participation in the study is not in the subject's best interest, including, but not limited to, concern that participation in the study has the potential to put the subject at undue risk or to interfere with the results of the study or the outcome measures.

4.3 Stopping Criteria

The DSMB will oversee the safety and tolerability of AP-PA02 during the study and determine if it is acceptable to continue. However, safety and tolerability data will be reviewed on an ongoing basis by the Medical Monitor and stopping rules will be applicable starting with dosing of the first subject.

4.3.1 Criteria for Potential Interruption or Discontinuation of Study Drug in Individual Subjects

In the event that any of the following criteria are encountered, the Investigator will review the AE with the Medical Monitor as soon as feasible. The Investigator will hold the next administration pending that review. The Investigator and Medical Monitor in consultation with the Sponsor will decide whether to continue to hold study treatment pending additional information or to discontinue study treatment.

- \geq Grade 3 AE or laboratory abnormality per Common Terminology Criteria for AEs (CTCAE) version 5.0 considered attributable to AP-PA02 (confirmed by unblinding). If the event or laboratory test is not listed in the CTCAE, the event or laboratory test should be graded by applying the CTCAE guidelines detailed in [Section 8.1.3](#);

Note: Clinically significant laboratory abnormalities classified per above should be confirmed with a repeat test within 24 hours.

- Any serious AE (SAE) considered attributable to AP-PA02 (confirmed by unblinding); or
- Acute bronchospasm, defined as a decrease in absolute FEV₁ of \geq 15% accompanied by symptoms requiring medical intervention, occurring from the Baseline value up to 4 hours following study drug administration and persisting following administration of a short-acting bronchodilator.

Any subject who prematurely discontinues from study drug, will have documented the reason and date of discontinuation in the electronic case report form (eCRF) and the subject should be encouraged to continue to complete all safety and key efficacy assessments at subsequent study visits. For subjects who do not agree to participate in subsequent study visits, study staff should make every effort to complete the full panel of assessments scheduled for the Early Termination (ET) Visit.

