5.2 Rationale for Dosing

5.3 Randomization and Blinding

A total of 24 eligible subjects will be randomized to Cohort A to receive either AP-PA02 or placebo (2:1 ratio) administered via inhalation. A total of 24 eligible subjects will be randomized to Cohort B to receive either AP-PA02 plus their current antipseudomonal inhaled antibiotic or placebo plus their current antipseudomonal inhaled antibiotic (2:1 ratio) administered via

inhalation. Up to an additional 2 optional cohorts (up to 30 subjects in each cohort) may be included to evaluate different doses and durations of treatment after DSMB review.

This is a double-blind study. All subjects, Investigators, and study and Sponsor personnel involved in the conduct of the study will be blinded to subject treatment assignment. There will be a designated unblinded statistician who will generate and have access to the randomization code. The unblinded statistician and other personnel who may become unblinded will not otherwise participate in any study procedures.

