5.4 Breaking the Blind

Unblinding at the request of the Investigator should occur only in the event of a severe AE or SAE that is reasonably assessed as treatment related and for which it is necessary to know the treatment assignment to determine an appropriate course of therapy for the subject. If the Investigator must identify the treatment assignment of an individual subject, the Investigator or qualified designee should request the treatment assignment from the centralized randomization system. They should not attempt to get this information from the site's unblinded study team. The Investigator is advised to not reveal the treatment assignment to any other site, Sponsor, or Contract Research Organization personnel.

Whenever possible, prior to proceeding with unblinding, the Investigator will contact the Sponsor to discuss the need to break the blind. The Investigator will notify the Sponsor as soon as is practical in the event of the study blind being broken and will document the reason. In the event this is not possible, the Investigator should contact the Sponsor as soon as possible to discuss the event without revealing the treatment assignment. The Investigator must document the subject identification, the date and time of breaking the blind, and must clearly explain the reasons for breaking the blind.

Medically necessary care should not be delayed for unblinding information (ie, the Investigator should treat the subject based on the subject's signs/symptoms without waiting for the unblinding process to be completed).

Subjects who are unblinded and discontinue study drug should continue to complete all safety assessments at subsequent study visits.

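### Protocol 4.3.1 makes two of its three mandatory dose-hold criteria depend on unblinding, although those who must act are blinded and only the Investigator has a conditional route to the assignment

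*Protocol*

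**What the plan says.** Protocol 4.3.1 sets out what happens when an individual subject meets a stopping criterion. The Investigator reviews the event with the Medical Monitor as soon as feasible, and meanwhile "The Investigator will hold the next administration pending that review". Then "The Investigator and Medical Monitor in consultation with the Sponsor will decide whether to continue to hold study treatment" or to discontinue it. There are three criteria: a Grade 3 or higher AE or laboratory abnormality, an SAE, and acute bronchospasm. The first two count only when "considered attributable to AP-PA02 (confirmed by unblinding", in the Protocol's parenthesis. The bronchospasm criterion carries no attribution test.

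Section 5.3 states: "All subjects, Investigators, and study and Sponsor personnel involved in the conduct of the study will be blinded to subject treatment assignment". Section 5.4 says that unblinding at the Investigator's request "should occur only in the event of a severe AE or SAE that is reasonably assessed as treatment related". A second condition applies as well: the choice of treatment for that subject must turn on knowing the arm. The request goes from the Investigator or a qualified designee to the central randomization system. Section 5.4 adds: "The Investigator is advised to not reveal the treatment assignment to any other site, Sponsor, or Contract Research Organization personnel". It also tells the Investigator not to let necessary care wait for the code, and says: "Subjects who are unblinded and discontinue study drug should continue to complete all safety assessments at subsequent study visits".

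**The concern.** A mandatory safety hold should rest on facts that the person applying it has at the time. Here the fact required is the treatment assignment, which that person is not meant to know. No section says who performs the check for 4.3.1, how quickly, or how the Medical Monitor and Sponsor learn the result before they join the decision.

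Two things are at stake. One is timing: a hold that waits for the code may come after the next dose. The other is the blind: if the site breaks the code to satisfy the criterion, the Investigator then assesses the rest of that subject's adverse events knowing the arm. Safety is part of the primary objective, and SAP 11.1 classes an event as drug-related from the recorded relationship attribution.

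**Working it through.** No figure in the plan depends on this point, so the check compares the sections, with a few counts.

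**1. The trigger.** Of the 3 criteria in 4.3.1, 2 carry the unblinding condition. The condition sits inside the criterion, and the hold follows only once a criterion is encountered. On the literal text, confirmation comes first and the hold second.

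**2. Who acts and what each can know.**

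| Role in the 4.3.1 decision | Status under 5.3 | Route to the assignment under 5.4 |
|---|---|---|
| Investigator | Blinded, named | Yes, or through a designee, if the event is a severe AE or SAE assessed as related and the assignment is needed to choose therapy |
| Medical Monitor | Blinded as Sponsor-side personnel (not named in 5.3, but 4.3.2 and SAP 8.7 call the role the Sponsor's) | None given |
| Sponsor | Blinded, named | None given; the Investigator is advised not to disclose |

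Confirming a hold criterion is not among the stated reasons for a code break.

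**3. Timing.** Section 5.5.3 puts the two daily administrations 6 hours apart on Day 1 and 10 to 12 hours apart on other days. If morning doses are taken at the same clock time (my assumption), the overnight gaps are 24 − 6 = 18 hours after Day 1 and 24 − 12 = 12 to 24 − 10 = 14 hours after later days. The longest gap, 18 hours, is shorter than the 24 hours that 3.1.1 allows for reporting a related Grade 3 or higher event to the Medical Monitor. While dosing continues, that reporting window therefore contains at least one scheduled dose. The documents set no time limit for the code break itself.

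SAP 8.6 expects 20 administrations in a full course. Section 5.5.3 places 4 in the clinic (two on Day 1, one each on Days 5 and 10), leaving 20 − 4 = 16 at home for a subject comfortable with home dosing. Most doses would go ahead unless someone tells the subject to stop.

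**4. If the code is broken instead.** The arm is unknown until checked, so every candidate event needs a check, including those in placebo subjects. At 2:1 randomization of 24 per cohort, 24 × 1/3 = 8 are on placebo. If candidate events were equally frequent per subject in both arms (an assumption; the documents give no rates), about one third of the code breaks would be in placebo subjects, for whom the criterion then turns out not to apply. Each break affects later causality judgements for one subject.

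**5. Neighbouring rules.** The sentinel rule in 3.1 acts on events assessed as treatment-related. The 24-hour report in 3.1.1 acts on the Investigator's assessment of relatedness. Neither requires the code, so the two 4.3.1 criteria are out of line with the Protocol's own practice.

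**The case against.** The strongest reply is that 4.3.1 and 5.4 can be read together. The 5.4 condition closely parallels the two criteria. A hold can fairly be seen as part of choosing therapy, and 5.4 expressly foresees subjects who are unblinded and stop study drug. It also has the Investigator contact the Sponsor beforehand where possible, and it says that necessary care must not wait for the code. Beyond that, 4.4 lets the Investigator, with Medical Monitor or Sponsor concurrence, discontinue or modify participation for any AE regardless of attribution. The Medical Monitor reviews data continuously under 4.3, and 3.1.1 covers acute events whatever their cause. Limiting holds to active-drug events may also be deliberate, to avoid interrupting placebo subjects.

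Much of this stands. It lowers the practical risk, and one Investigator unblinded for one subject is the ordinary result of any code break. But these routes are discretionary or concern care and reporting in general. None converts the conditional hold into a mandatory one. If the intention is to hold first and confirm later, the text does not say so.

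Several stronger readings are tempting but unsupported:

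- *That nobody can obtain the assignment.* The Investigator can, conditionally.
- *That the joint decision can make no use of the code.* The non-disclosure wording is advice, and the Investigator is one of the deciders.
- *That laboratory abnormalities fall outside 5.4.* Section 8.1 counts abnormal laboratory findings as AEs, and 8.1.3 describes Grade 3 as severe.
- *That 8.1.3 sets too strict a causality standard to use here.* Its related category includes possibly related events, and it speaks of a reasonable possibility.
- *That 4.3.2 has the same fault.* Two of its three triggers carry the same parenthesis, but they go to a DSMB that reviews unblinded data under a Charter not among these documents.
- *That the number of later spirometry visits measures the harm.* That would be a schedule count, not a size of bias.

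**Conclusion.** The conflict in 4.3.1 is real, and mending it is a cheap improvement. Two of the three individual hold criteria rest on a fact that the people applying them are not meant to know, and the only route to it is conditional, open to the Investigator alone, and not designed for this purpose. Followed to the letter, the rule either puts the mandatory hold behind a code break, with the next dose 6 hours away on Day 1 or 10 to 12 hours away within other days, or unblinds the Investigator for each candidate event.

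Confidence is high on the textual clash and lower on its consequences. The documents give no event rate and no turnaround time for a code break, so I put no number on late holds, missed holds or bias in attribution. A reader might infer an effect on the primary endpoint; nothing here supports that, since sputum cultures are processed at a central laboratory. The conclusion assumes that the Medical Monitor is covered by the blinding sentence in 5.3, which does not name the role.

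**What to change.** In the first two criteria of 4.3.1, delete the parenthesis about unblinding and replace the attribution to AP-PA02 with: *assessed by the Investigator, while blinded, as at least possibly related to study treatment (a reasonable possibility)*. The first criterion already covers laboratory abnormalities, so nothing more is needed for them. The wording agrees with the sentinel rule in 3.1, the reporting rule in 3.1.1 and the definition of a drug reaction in 8.1.1. Leave 5.4 as it is, for code breaks needed to choose therapy.

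The cost is a wording change in two criteria. The downside is that some placebo subjects whose events are judged related will have dosing held until the review with the Medical Monitor; under the equal-rate assumption above, that would be about one in three of the subjects held. In return, the hold can take effect at once and does not require breaking the blind.
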